5.1 Method of Assigning Subjects to Treatment Groups

Subjects will be randomly assigned to 1 of 3 treatment groups, in a 1:1:1 ratio, as presented in Table 3-1, and operationally managed to maintain a minimum number of subjects enrolled in 2 age groups: 6 to 10 years, inclusive; and 11 to 17 years, inclusive. A staggered enrolment is planned: the first 45 subjects enrolled will be in the older age group of 11 to 17 years, inclusive, and designated the safety lead-in cohort. After reactogenicity for the safety lead-in cohort is reviewed by the medical monitor, medical lead, and SMC chairman (with appropriate consultation with investigators, if needed), the remainder of subjects will be enrolled. An interactive response technology (IRT) system will be used to administer the randomization schedule centrally. The IRT system will also be designed to distribute the full cohort into groups to provide mid-turbinate/nasopharyngeal samples for *B. pertussis* culture or PCR on Day 29 or 85; however, if a subject cannot provide a sample on Day 29 (for any reason), the subject should provide a sample on Day 85 (this will not be considered a protocol deviation). Biostatistics will generate the randomization schedule using SAS® software Version 9.3 or later (SAS Institute Inc, Cary, North Carolina) for the IRT, which will link sequential subject randomization numbers to treatment codes. The randomization schedule will be created by the dedicated randomization team, stored in a separate project area, and will be blinded to the project team with the exception of an unblinded team who will manage vaccine logistics, preparation, and administration, but will not be involved in

study-related assessments or have subject contact for data collection following study vaccination.

Enrolled subjects may participate in an optional substudy in which subjects may elect to participate at any time from the day of enrolment through Day 85. No randomization is planned for the substudy as all subjects participating in the open-label substudy will receive an intranasal re-vaccination/attenuated challenge with BPZE1 on Day 85. It is recognized this may introduce some subject bias due to the opt-in nature, but this has been deemed acceptable by the sponsor.

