- ^c Subjects not participating in the substudy are to complete procedures listed under Study Visit V3 for Day 85. Subjects in the safety lead-in cohort who are not participating in the substudy are not required to provide samples on Day 85 and may complete this visit remotely.
- ^d Subjects participating in the substudy (only) to complete procedures listed under Study Visits SSV3, SSV4, SSV5, and SSV6.
- ^e Procedures listed for an Unscheduled study visit are optional and dependent on the cause for the visit itself. An unscheduled study visit may occur at any time between enrolment and Day 169/EOS.
- ^f Reviewed and/or updated.
- ^g Performed prior to vaccination.
- ^h Such as date of birth (where allowed by local regulations), sex, race, ethnicity, weight, and height (with derived BMI and Z-score).
- ⁱ Including prior and ongoing chronic medical conditions and past surgeries.
- ^j Concomitant medications will include all medications and OTC products (including herbal supplements and multivitamins) taken by the subject from the time of signing the ICF through Day 29 (and from Day 85 [following study vaccination] through Day 113 for subjects participating in the optional substudy), or through an early termination visit, if prior to these time points. The use of anti-pyrogenic medication will be specifically queried by diary during the 7 days following any study vaccination.
- ^k Only concomitant medications associated with any MAAE (through 84 days following any study vaccination); or AESI or SAE (through Day 169/EOS) will be recorded.
- ^l Vaccines received outside of the study will be specifically queried during each visit and recorded through Day 169/EOS.
- ^m Targeted physical examination at screening and Day 1 (prior to vaccination) to include head and neck (inclusive of nasal cavity and oropharynx), respiratory, cardiac, abdomen, and lymph nodes associated with the upper extremity, head, and neck. Targeted physical examination at all other times will be symptom-directed and performed at the discretion of the investigator. Height and weight will be measured at screening only.

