3.2.3. Exploratory Endpoints

3.2.3.1. Mucosal Secretory Immunogenicity (Optional Substudy Only)

Note that S-IgA objectives and endpoints for the overall study (as noted above) will also be analyzed for the optional substudy and will be considered exploratory.

- Induction of mucosal S-IgA at Day 29 or 85 (tested independently) compared by protection against colonization (Colonizers/Non-colonizers) by treatment group (BPZE1, BPZE1 + Boostrix, BPZE1 and BPZE1 + Boostrix, Boostrix control).
- Induction of mucosal S-IgA (WCE, FHA, PRN and any additional anti-pertussis mucosal antibodies identified during assay development) at Day 113 compared with Day 85 following BPZE1 attenuated challenge by treatment group (BPZE1, BPZE1 + Boostrix).
- Induction of mucosal S-IgA at Days 113 and 169/EOS (tested independently) in subjects who participated in the substudy compared with subjects who did not participate in the substudy by treatment group.

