8.4.2. Analysis of Mucosal Secretory Immunogenicity Endpoints

BPZE1, BPZE1 + Boostrix, BPZE1 and BPZE1 + Boostrix, and Boostrix control induction of mucosal S-IgA at Days 29 and 85 will be summarized by protection against colonization (Colonizers/Non-colonizers) and by treatment group and by timepoint. Separate two-sample t-tests will be used to compare the natural log-transformed GMRs at Days 29 and 85 between Colonizers and Non-colonizers by treatment group and by timepoint.

To test the hypothesis that BPZE1 and BPZE1 + Boostrix can induce mucosal S-IgA at Day 113 compared with Day 85, separate paired t-tests will be used to compare the natural log-transformed GMCs/GMRs at Day 113 with the natural log-transformed GMCs/GMRs at Day 85 within each treatment group. The corresponding 95% CIs will be calculated on the natural log scale, then both lower and upper limits will be exponentiated to get the 95% CIs on the original scale.

BPZE1, BPZE1 + Boostrix, or Boostrix control induction of mucosal S-IgA at Day 113 and Day 169/EOS will be summarized by participation in the substudy (Yes/No) and by treatment group and by timepoint. Separate ANCOVA models that include baseline S-IgA and an indicator of participation in the substudy (Yes/No) as covariates will be used to compare between subjects who participated in the substudy and subjects who did not participate in the substudy, by treatment group and by timepoint.

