8.4.3. Analysis of Serum Immunogenicity Endpoints

To test the hypothesis that BPZE1 induction of serum immunity (IgA, IgG) at Day 113 compared with baseline, or Day 113 compared with Day 85, separate paired t-tests will be used to compare the natural log-transformed GMC at Day 113 with the natural log-transformed GMC at either baseline or Day 85 within each treatment group (BPZE1, BPZE1 + Boostrix, Boostrix). The corresponding 95% CIs will be calculated on the natural log scale, then both lower and upper limits will be exponentiated to get the 95% CIs on the original scale.

BPZE1, BPZE1 + Boostrix, and Boostrix induction of serum immunity (IgA, IgG) at Day 113 and Day 169/EOS will be summarized by participation in the substudy (Yes/No) and by treatment group and by timepoint. Separate two sample t-tests will be used to compare the natural log-transformed GMCs at Day 113 and Day 169/EOS between subjects who participated in the substudy and subjects who did not participate in the substudy (Day 169/EOS only), by treatment group and by timepoint.

BPZE1, BPZE1+Boostrix, BPZE1 and BPZE1+Boostrix, Boostrix control induction of serum immunity (IgA, IgG) at Days 29 and 85 will be summarized by protection against colonization (colonized/non-colonized) and by treatment group and by timepoint. Comparison between colonized subjects and non-colonized subjects will be made using separate two-sample t-tests by treatment group and by timepoint.

The number and proportion of subjects with $\geq 50\%$ killing titer (or equivalent) at Day 113 compared to baseline and Day 29 will be summarized by treatment group and by timepoint. The 95% CI will be provided by using Agresti-Coull method. A McNemar test will be used to compare proportions between timepoints in each treatment groups (Day 113 vs baseline; Day 113 vs Day 29).

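### The serum comparison of substudy volunteers with non-volunteers at Day 169 omits the baseline adjustment used for its S-IgA counterpart, and the S-IgA comparison is also planned at Day 113, where non-volunteers have no sample

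*SAP*

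**What the plan says.** **Serum (SAP 8.4.3).** Within each treatment group, "Separate two sample t-tests will be used to compare the natural log-transformed GMCs at Day 113 and Day 169/EOS" between the two participation groups. No covariate is named. The same sentence restricts one side: "subjects who did not participate in the substudy (Day 169/EOS only".

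**S-IgA (SAP 8.4.2).** The same split is analysed differently: "Separate ANCOVA models that include baseline S-IgA and an indicator of participation in the substudy (Yes/No) as covariates will be used", by treatment group and timepoint. The timepoints are both days: "induction of mucosal S-IgA at Day 113 and Day 169/EOS will be summarized by participation in the substudy (Yes/No". There is no Day 169-only limit. Endpoint 3.2.3.1 repeats both days: "Induction of mucosal S-IgA at Days 113 and 169/EOS (tested independently) in subjects who participated in the substudy compared with subjects".

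**Who is in each group.** SAP 4.2 plans no randomization for the substudy; subjects elect to join at any time up to Day 85. Protocol 5.1 comments: "It is recognized this may introduce some subject bias due to the opt-in nature", and adds that the sponsor finds this acceptable.

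**Who is seen at Day 113.** Day 113 is visit SSV6. Footnote d of the Schedule of Events (Protocol 13.1, repeated in SAP 13.1) reads: "Subjects participating in the substudy (only) to complete procedures listed under Study Visits SSV3, SSV4, SSV5, and SSV6". Blood for immunogenicity is scheduled for all subjects before vaccination on Day 1 and again at Day 169/EOS.

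**The concern.** The question is whether a second BPZE1 dose changes later antibody levels. Volunteers and non-volunteers were not randomized to the two sides, so a difference in antibody level that existed before the first vaccination carries through to Day 169. An unadjusted test would attribute it to re-vaccination. The SAP guards against the measured part of this for S-IgA but not for serum, and gives no reason for the difference. Leaving out the baseline also gives up precision in a comparison that may have about 36 subjects on its smaller side in each arm.

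The Day 113 problem is of another kind. A contrast with no subjects on one side gives no result, so part of a stated objective and a planned table cannot be delivered.

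**Working it through.** **1. The plan's own figures.** The documents give no sample size or power for the participation comparison. SAP Table 4-2 supplies standard deviations for ln serum IgG: PT 0.8759, FHA 0.8158, PRN 1.4363. As a check on these inputs, I recomputed its non-inferiority power with 108 per group, margin 0.693 and one-sided 0.025. The noncentrality is (0.693 + difference) / (SD × √(2/108)).

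| Antigen | Difference | Power, recomputed | Power, stated |
|---|---|---|---|
| PT | -0.234 | 96.95% | 97.0% |
| FHA | -0.019 | 100% | 100% |
| PRN | -0.075 | 88.25% | 88.2% |

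The table reproduces. This validates the inputs only; it does not bear on the point itself. These SDs serve the Day 29 power calculation, so using them at Day 169 is an assumption.

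**2. Precision of the participation comparison.** Up to 120 of about 360 subjects may join. Assuming even uptake, that is 40 against 80 per arm, or 36 against 72 after 10% dropout. The 95% half-width is t(0.975, 106) × SD × √(1/36 + 1/72):

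- PT: 0.354 ln units, a ratio factor of 1.43
- FHA: 0.330, factor 1.39
- PRN: 0.581, factor 1.79

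**3. What baseline ANCOVA gains.** With r the correlation of ln baseline and ln Day 169 value (assumed), the variance ratio to the unadjusted analysis is 1 − r².

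- r = 0.5: ratio 0.75, variance down 25%; √0.75 = 0.866, interval width down 13%
- r = 0.7: ratio 0.51, variance down 49%; √0.51 = 0.714, interval width down 29%

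**4. Bias left in the unadjusted estimate.** Bias = slope × difference in ln baseline. Both inputs are assumptions.

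- Baseline GMT 10% apart, slope 0.3: 0.3 × ln 1.1 = 0.029, about 3%
- Baseline GMT 30% apart, slope 0.7: 0.7 × ln 1.3 = 0.184, about 20%

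**5. Effect on the false-positive rate.** Suppose re-vaccination has no effect and the split is 36 against 72. A baseline difference of d SDs shifts the test's noncentrality to r × d / √(1/36 + 1/72). For r from 0.3 to 0.7 (assumed), the nominal 5% two-sided rate becomes:

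- d = 0.2: 6.0% to 10.4%
- d = 0.5: 11.3% to 39.7%

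At d = 0.5 and r = 0.5 the spurious GMC ratio is exp(0.25 × 0.8759) = 1.24 for PT and exp(0.25 × 1.4363) = 1.43 for PRN.

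**6. S-IgA at Day 113.** The 8.4.2 model has an intercept, baseline and a participation indicator. At Day 113 every subject is a participant, so the indicator equals the intercept and the design matrix has rank 2 of 3. The participation effect is not estimable. At Day 169 the rank is 3 of 3. The windows in SAP 4.5 offer no way round this: Day 113 is not applicable in the main study, and a main-study sample from Day 58 to Day 127 is assigned to Day 85.

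**The case against.** The strongest reply is that little hangs on this. SAP 3.2.3 classes both comparisons as exploratory, with no success criterion attached. Protocol 5.1 discloses the opt-in bias. The Day 113 contrast cannot mislead anyone because it cannot be computed; it lacks a limit that 8.4.3 already carries. All of this stands and keeps the severity low. Disclosure is still no reason to leave out a covariate that is already collected.

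Nor is the SAP uniform elsewhere: 8.3.1 tests BPZE1 against Boostrix on S-IgA by a two-sample t-test, and 8.3.2 does so for functional antibody. Those, however, compare randomized arms. For serum IgA and IgG at Day 169, 8.3.2 itself uses baseline ANCOVA between randomized arms, where the need is smaller.

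Four stronger readings are tempting, and the documents do not support them:

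- *The serum test is also impossible at Day 113.* The first half of its sentence suggests so, but the sentence goes on to limit non-participants to Day 169/EOS.
- *Bias has been shown.* The documents do not show that volunteers differ at baseline, or in which direction. Protocol 5.1 concedes a possibility for the substudy in general. Every bias figure above is conditional on assumed inputs.
- *Baseline ANCOVA cures the self-selection.* Opt-in runs to Day 85, so subjects may choose on events after Day 1 or on factors never measured. Adjustment removes only the part carried by measured baseline.
- *The paired Day 113 versus Day 85 test answers the Day 113 objective.* It has no concurrent non-participants, and for S-IgA the SAP's hypothesis names only the two BPZE1 arms, whereas the participation comparison includes Boostrix.

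**Conclusion.** Both parts hold, at low severity. The serum comparison at Day 169/EOS is unadjusted on a self-selected split, while the SAP adjusts the S-IgA counterpart and the same serum outcomes between randomized arms. On the assumed ranges, adjustment narrows the interval by 13% to 29% and removes a distortion of about 3% to 20%. Correlation, slope, baseline difference and uptake per arm are assumptions; the documents give none of them. The Day 113 S-IgA contrast between participants and non-participants is not estimable as planned, and this part rests on no assumption. Primary and key secondary conclusions are unaffected.

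**What to change.** 1. **SAP 8.4.3:** replace the two-sample t-tests with the 8.4.2 model: ln Day 169/EOS IgA or IgG on ln baseline value and a participation indicator, by treatment group. SAP 4.3.3 already requires a baseline result for the test being analysed, so no subject is lost.
2. **Day 85 value:** keep it out of the main model. Lead-in subjects outside the substudy need not give a Day 85 sample, so requiring it would lose data mainly from the non-participant side.
3. **SAP 8.4.2 and endpoint 3.2.3.1:** limit the S-IgA participation comparison to Day 169/EOS.
4. **Alignment:** bring the Day 113 wording in 2.3.1, 2.3.2, 3.2.3.2 and the Yes/No summaries in 8.4.2 and 8.4.3 into line. Describe the Day 113 response within participants (Day 113 versus Day 85) and say that this does not replace a concurrent comparison.
5. **Reporting:** state beside the result that participation was chosen, and that selection on unmeasured factors or on events up to Day 85 remains.

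The cost is SAP wording and one model statement, with no new data. It should be done before the data are unblinded, so that the model change is not post hoc.

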Note that serum IgA and IgG objectives and endpoints for the overall study (as noted above) will also be analysed for the optional substudy and will be considered exploratory.

Exploratory objectives	Exploratory endpoints

 To measure BPZE1 induction of serum immunity at Day 113; and to assess if induction of a boost response (relative to Day 85 response) is observed for those subjects with prior BPZE1 vaccination (BPZE1, BPZE1 + Boostrix). 	
 BPZE1, BPZE1 + Boostrix, and Boostrix induction of serum immunity (IgA, IgG) at Day 113 compared with baseline (by treatment group). BPZE1, BPZE1 + Boostrix, and Boostrix induction of serum immunity (IgA, IgG) at Day 113 compared with Day 85 (by treatment group).

 To assess if Day 113 response and longer-term immune durability through Day 169/EOS is altered with re-vaccination/attenuated challenge when compared to those subjects who did not participate in the substudy, relative to each randomized treatment group (BPZE1, BPZE1 + Boostrix, Boostrix). 	
 BPZE1, BPZE1 + Boostrix, and Boostrix induction of serum immunity (IgA, IgG) at Days 113 and 169/EOS in subjects who participated in the substudy compared with subjects who did not participate in the substudy (tested independently by treatment group and day).

 To assess if serum immunity of individual and combinations of pertussis antibodies (eg, WCE, PT, FHA, PRN, and any additional anti-pertussis antibodies) at Day 29 or 85 is relational to protection against colonization by treatment group and overall (BPZE1, BPZE1 + Boostrix, Boostrix). To assess functional antibody response by treatment group at Day 113 compared to baseline and Day 29, as measured by an appropriate assay for bactericidal activity. 	
 BPZE1, BPZE1 + Boostrix, BPZE1 and BPZE1 + Boostrix, Boostrix induction of serum immunity (IgA, IgG) at Day 29 or Day 85 compared by protection against colonization (Colonized/Non-Colonized) (tested independently by treatment group and overall). Proportion of subjects with $\geq 50\%$ killing (or equivalent) for functional antibody response at Day 113 compared to baseline and Day 29 (tested independently by treatment group and day).
Colonization (optional substudy only)	
Exploratory objective	Exploratory endpoints

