6.4 Immunogenicity and Colonization Assessments

Immune measurements will be conducted on serum (IgG and IgA) and nasal mucosal secretion (S-IgA) samples for anti-pertussis antibodies of WCE, PT, FHA, and PRN as well as any additional anti-pertussis antibodies included in assay development. Serum bactericidal activity (or other functional assays identified) will be measured in a subset of subjects.

Cellular-mediated response to BPZE1 and Boostrix (Th1/Th17 vs Th2) will be assessed by ELISpot or flow cytometry at baseline and Day 8 (safety lead-in cohort) and Day 85 and Day 113 (subset of substudy subjects). Additional testing for antigens specific to *B. pertussis* may be performed at a later date as BPZE1 induces broader immunity more similar to natural infection induced immunity and does not contain the purified antigen levels of PT, FHA, and PRN found in Boostrix. Mid-turbinate/nasopharyngeal samples will be evaluated by real-time PCR or by *B. pertussis* culture for colonization of BPZE1.

Subjects will consent for the use of samples for further anti-pertussis antibody testing or other assay development as part of the standard consenting process. Aliquots of collected samples from this study may be retained for additional testing of biological responses (eg, antibodies, T-cell responses, microbiome) specific to future development of BPZE1 and ILiAD Biotechnologies' *B-Tech* program for a maximum of 15 years (starting from the date at which the last subject had the last study visit), unless local rules, regulations, or guidelines require different time frames or different procedures, and in accord with subject consent.

Procedures for the handling and processing of immunogenicity samples are provided in the laboratory manual or the site manual.

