2.3.2. Serum Immunogenicity (Optional Substudy Only)

- To measure BPZE1 induction of serum immunity at Day 113; and to assess if induction of a boost response (relative to Day 85 response) is observed for those subjects with prior BPZE1 vaccination (BPZE1, BPZE1 + Boostrix).

- To assess if Day 113 response and longer-term immune durability through Day 169/EOS is altered with re-vaccination/attenuated challenge when compared to those subjects who did not participate in the substudy, relative to each randomized treatment group (BPZE1, BPZE1 + Boostrix, Boostrix).
- To assess if serum immunity of individual and combinations of pertussis antibodies (eg, WCE, PT, FHA, PRN, and other known anti-pertussis antibodies) at Day 29 or 85 is relational to protection against colonization by treatment group and overall (BPZE1, BPZE1 + Boostrix, Boostrix).
- To assess functional antibody response by treatment group at Day 113 compared to baseline and Day 29, as measured by an appropriate assay for bactericidal activity.

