of serum IgA and IgG is non-inferior to Boostrix at Day 85 and Day 169/EOS. An ANCOVA model that includes baseline IgA or IgG and treatment group as covariates will be used to compare the natural log-transformed GMCs at Day 85 and Day 169/EOS between either BPZE1 or BPZE1+Boostrix and Boostrix groups. The non-inferiority margin is set at a 2-fold decrease or -0.693 on natural log scale. Non-inferiority will be demonstrated if the lower limit of the 95% CI of group difference on natural log scale is greater than -0.693.

Subgroup analysis by age group (6-10 years and 11-17 years, inclusive, and 10 – 17 years [for requested analyses]), time since last aP vaccination prior to study entry (<median time, \geq median time), or other baseline demographics, and by baseline antibody level (by quantile) will be conducted to examine differential responses to induction of serum immunity (IgA, IgG) at Day 29 by treatment group (BPZE1, BPZE1+Boostrix, and Boostrix). In addition to descriptive summaries, a forest plot of the corresponding 95% CIs will be generated for each subgroup.

To compare BPZE1 and BPZE1 + Boostrix induction of measurable functional antibody (subset of subjects) with Boostrix at Day 29, separate two-sample t-tests will be used to compare between treatment group differences in natural log-transformed GMC at Day 29. The corresponding 95% CIs by treatment group will be calculated on the natural log scale, then both lower and upper limits will be exponentiated to get the 95% CIs on the original scale.

Seroconversion rates with 95% CIs for IgA and IgG will be calculated at Days 29 and 85 by treatment group and day. The 95% CI will be calculated by using Agresti-Coull method. The likelihood ratio chi-square test will be used to compare seroconversion rate between treatment groups. Additional combinations of antibody response (WCE, PT, FHA, PRN, and any additional anti-pertussis antibodies) may also be tested.

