The number and proportion of subjects with a $\geq 2x$ increase from baseline in SBA bactericidal titer (50% killing titer) will be summarized by treatment group, by timepoint and by strain. The 95% CIs for each treatment group will be computed using the Agresti-Coull method and the 95% CIs for the difference in proportions between groups (BPZE1 vs Boostrix, BPZE1 + Boostrix vs Boostrix) will be computed using Agresti Caffo method. A chi-square test will be performed to compare the proportion of subjects between groups (BPZE1 vs Boostrix, BPZE1 + Boostrix vs Boostrix) with a $\geq 2x$ increase in SBA bactericidal titer and two-sided p-value will be provided.

Reverse cumulative distribution curves will be provided for SBA (PRN+ and PRN-) at baseline, Day 29 and Day 113.

9. Safety Analysis

Unless otherwise specified, safety analysis will be performed based on the Safety Analysis Set. Safety analysis for safety lead-in cohort will be performed based on the Safety Lead-in Analysis Set. All summaries and analyses will be presented by treatment groups (BPZE1, BPZE1 + Boostrix, Boostrix), age group, and overall for first study vaccination and following re-vaccination/attenuated challenge (substudy) separately.

9.1.Solicited Adverse Events

The number and percentage of subjects with any solicited AEs (local, nasal/respiratory, and systemic reactogenicity events) through 7 days following first study vaccination with any

combination of pertussis-containing vaccines (BPZE1, BPZE1 + Boostrix, Boostrix) will be calculated by treatment group, age group and overall, and by timepoint.

Solicited reactogenicity events occurring from the time of study vaccination on Day 1 for 7 consecutive days starting the day following study vaccination, including local, nasal/respiratory reactions and systemic reactogenicity, will be summarized as presenting both the number and frequency, categorized by the severity grades according to respective reactogenicity grades (Table 9-1-1, Table 9-1-2, and Table 9-1-3).

Additionally, solicited AEs will be analyzed by determining the maximum severity through 7 days following study vaccination on Day 1 to summarize the frequency and percentage of subjects reporting each local, nasal/respiratory, or systemic event.

Redness measurements, swelling measurements, and oral temperature if subjects have fever for 7 days following vaccination will be summarized using descriptive statistics.

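### Functional antibody over time is tested only as a yes/no at 50% killing, and the Day 29 between-arm titre test leaves out the baseline titre

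*SAP*

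**What the plan says.** **Over time, within arm.** The exploratory substudy objective in SAP 2.3.2 is: "To assess functional antibody response by treatment group at Day 113 compared to baseline and Day 29". Protocol 2.2 defines the endpoint as the proportion of subjects with at least 50% killing, "for functional antibody response at Day 113 compared to baseline and Day 29 (tested independently by treatment group and day". SAP 8.4.3 tests it this way: "A McNemar test will be used to compare proportions between timepoints in each treatment groups (Day 113 vs baseline; Day 113 vs Day 29". No other SBA test over time is named.

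**Between arms, SAP 8.4.3.** A responder is a subject whose 50% killing titre at least doubles from baseline. Responders are summarised by visit and strain, and: "A chi-square test will be performed to compare the proportion of subjects between groups (BPZE1 vs Boostrix, BPZE1 + Boostrix vs Boostrix". The section also plans a display with no test attached: "Reverse cumulative distribution curves will be provided for SBA (PRN+ and PRN-) at baseline, Day 29 and Day 113".

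**Between arms, Day 29, SAP 8.3.2.** For the secondary endpoint the aim is: "To compare BPZE1 and BPZE1 + Boostrix induction of measurable functional antibody (subset of subjects) with Boostrix at Day 29". The method is: "separate two-sample t-tests will be used to compare between treatment group differences in natural log-transformed GMC at Day 29". No covariate is listed.

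**Size of the data.** Protocol 6.4 says: "Serum bactericidal activity (or other functional assays identified) will be measured in a subset of subjects". The subset size is not given. Day 113 samples come only from the substudy, which is capped at 120 children (Protocol 3.1.1), or about 40 per arm if opt-in is balanced.

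**The concern.** The SAP treats SBA as a titre: it defines a two-fold rise in the 50% killing titre, plots the titre distribution, and in 8.3.2 compares functional antibody on the natural log scale. Baseline is measured. Yet the test over time uses only whether a child crosses one cut.

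McNemar's test counts only children who change side. A child above the cut at both Day 29 and Day 113 adds nothing, however far the titre has risen. If Boostrix or BPZE1 has already taken most children over the cut by Day 29, the Day 113 versus Day 29 test has almost nothing to work with. A non-significant result could then be read as no functional boost from the Day 85 dose.

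The Day 29 between-arm t-test keeps the titre whole, but it leaves baseline variation in the error term. The SAP removes that variation for IgG and IgA.

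**Working it through.** **1. The SAP's own tests side by side**

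| Comparison | IgG / IgA | Functional antibody |
|---|---|---|
| Within arm, Day 113 vs baseline | paired t on ln concentration (8.4.3) | McNemar on at least 50% killing (8.4.3) |
| Within arm, Day 113 vs an earlier post-dose visit | paired t on ln concentration, vs Day 85 (8.4.3) | McNemar, vs Day 29 (8.4.3) |
| Between arms, Day 29 | ANCOVA with baseline (8.2 for IgG, 8.3.2 for IgA) | two-sample t on ln scale, no baseline (8.3.2) |
| Between arms, Day 113 | none named | chi-square on two-fold rise (8.4.3) |

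No reason is given for the different treatment.

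**2. Check of the method.** No SBA power is stated, so there is no SBA figure to reproduce. The stated primary power does reproduce: noncentrality 0.35 × √108 = 3.64 gives 95.0% (stated 95%), and 0.950² = 90.2% (stated 90%).

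**3. Within arm.** Assumptions: ln titres bivariate normal with equal SD at both visits, n = 40, correlation 0.6, true rise 0.5 SD, two-sided 0.05.
- Paired t: SD of the difference = √(2 × (1 − 0.6)) = 0.894 SD. Standardised rise = 0.5 / 0.894 = 0.559. Noncentrality = 0.559 × √40 = 3.54. Power is about 93%, whatever the share positive.
- McNemar, 50% positive at Day 29: under the bivariate normal, 25.7% cross upward and 6.5% downward, or 10.3 and 2.6 children of 40. The statistic at these expected counts is (10.3 − 2.6)² / (10.3 + 2.6) = 4.6, just above the critical 3.84.
- McNemar, 90% positive: 8.1% and 1.8% cross, or 3.2 and 0.7 children. The statistic is (3.2 − 0.7)² / (3.2 + 0.7) = 1.6, well below 3.84.

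**4. With an assay floor.** SAP Section 4 sets results below the detection limit to half that limit, which weakens a t-test when many values are low. The unfavourable case puts the floor at the cut itself (ln SD 1.2 assumed). McNemar does not change, because the floor does not alter who is above the cut. Simulated power, accurate to a point or two:

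| Positive at Day 29 | Paired t, no floor | Paired t, floor at cut | McNemar |
|---|---|---|---|
| 10% | 93% | 44% | 38% |
| 30% | 93% | 75% | 56% |
| 50% | 93% | 86% | 59% |
| 70% | 93% | 90% | 46% |
| 90% | 93% | 92% | 21% |

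With the floor, the gain runs from about 6 points (44 − 38) to about 70 (92 − 21 = 71).

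**5. Between arms, Day 29.** Assumptions: n = 40 per arm, true difference 0.5 SD.
- Planned t-test: noncentrality 0.5 / √(2/40) = 2.24, power about 60%.
- ANCOVA: noncentrality 2.24 / √(1 − r²), that is 2.34, 2.58 and 2.80 at r = 0.3, 0.5 and 0.6, for power of about 64%, 72% and 79%. Simulation also counts chance imbalance in baseline and gives gains of about 3, 12 and 17 points.
- Two-fold-rise chi-square at r = 0.6, with ln SD 1 and a common rise of 0.5: about 54%.

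**6. Wider range.** Assumptions: 15 to 40 per arm, ln SD 0.8 to 1.44 (guided by the IgG SDs in SAP Table 4-2), correlation 0.3 to 0.7, no floor. For the within-arm test, 10% to 70% positive at the start and rises of 1.5- to 3-fold.
- Paired t minus asymptotic McNemar: 0 to 61 points, median 26.
- ANCOVA minus the planned Day 29 t-test: 0 to 29 points, median 7.
- ANCOVA minus the two-fold-rise chi-square: 2 to 37 points, median 22.

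**The case against.** - **The protocol defines the Day 113 endpoint as a proportion, and it is exploratory.** McNemar is a standard test for a paired proportion. This stands: it is a reason to keep McNemar, but not to leave out the titre. The two-fold-rise test and the distribution curves already go beyond that endpoint.
- **A shift in titre would be seen anyway.** The distribution curves and the two-fold responder rates would show movement above the cut. SAP Section 4 also promises geometric means and fold rises with confidence intervals for serum immunogenicity. If that covers SBA, which is arguable, the Day 113 versus baseline interval is already there. Baseline is Day 1, so Day 113 versus Day 29 would still lack one.
- **The explicit boost objective lies elsewhere.** It concerns serum immunity relative to Day 85, tested by paired t on IgA and IgG. Study success rests on the two S-IgA comparisons alone. Both statements are correct and limit the harm.
- **The gain depends on unknown inputs.** With few children positive at Day 29 and a floor at the cut, the paired test adds little. With a large rise, both tests succeed.

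A reader might also infer that SBA is compared between arms only as a responder rate. The documents do not support that: SAP 8.3.2 tests functional antibody on the log scale at Day 29. The responder cut stands alone only at Day 113.

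**Conclusion.** The point holds for three specific gaps. Change in SBA over time is tested only as threshold crossing. At Day 113 the arms are compared only on a two-fold rise. The Day 29 log-scale comparison omits a baseline that the SAP uses for IgG and IgA.

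That McNemar cannot register a rise above the cut follows from the test itself and needs no assumption. The size does need assumptions, because the documents give no SBA subset size, SD, correlation or positivity. At n = 40, correlation 0.6 and a 0.5 SD rise, the paired test gains from about 6 points (10% positive, floor at the cut) to about 70 (90% positive). Baseline adjustment at Day 29 gains about 3 to 17 points for correlations of 0.3 to 0.6.

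A reader might infer a general loss of 20 to 70 points for all SBA tests. That is not supported: gains of that order apply only to McNemar and only in some scenarios, while the between-arm gains are smaller. Nor do the documents support calling McNemar wrong or dropping it. The matter touches one secondary and one exploratory endpoint, not the success criterion.

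**What to change.** 1. In SAP 8.3.2, replace the unadjusted Day 29 functional-antibody t-test with an ANCOVA of ln titre on treatment and ln baseline titre. Apply the same model at Day 113.
2. In SAP 8.4.3, add paired t-tests on the ln 50% killing titre for Day 113 versus baseline and Day 113 versus Day 29. Report the geometric mean fold rise with its 95% confidence interval, by arm and strain.
3. Keep the protocol-defined proportion with at least 50% killing and its McNemar test, and keep the two-fold responder rates.

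The cost is SAP wording and a few extra outputs. The titres and baseline samples are already planned, and no protocol endpoint is removed.
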